## **DATA COLLECTION AND MANAGEMENT**

All study data will be recorded by research staff and securely maintained at primary site.

Data will be entered by study staff into REDCap database that will be stored on a secure server.

Each patient will have a unique identification number to which only the principal and co-investigators will have access. The data collection spreadsheet will not contain any patient identifiers and will be password protected. The master list that links the patients and their study identification number will be stored separately from the database. All collected information will be stored separately on a password protected hard drive. A back up copy of the file will be stored on a password protected hospital network drive. All hard copies of study data will be stored in a locked cabinet in the office of the research nurse, which will also be locked.

## **OUTCOME MEASURES**

### **Primary Hypothesis**

The primary hypothesis is that the administration of nitrofurantoin will reduce the UTI rate compared to the UTI rate in the placebo arm upon discontinuation of catheterization. The null hypothesis is that the administration of nitrofurantoin will not reduce the rate of UTI.

### **Primary Outcome Measure**

The primary outcome of the study will be the treatment of symptomatic urinary tract infection and rate of urinary tract infection in the first 30 days following pelvic reconstructive surgery.

### **Secondary Outcome Measures**

1. Adverse Events
  - a. Any adverse event related to drug administration will be reported. Adverse events not related to medication administration will not be collected. Please refer to section on Adverse Events for details of reportable criteria.
2. Medication compliance
  - a. All participants will need to complete a medication diary during the study drug treatment period. They will be asked to return this diary at their follow up. Medication compliance will be assessed and analyzed by way of these medication diaries.

## **STATISTICAL CONSIDERATIONS**

Calculations of sample size were based on comparisons of UTI rates in the nitrofurantoin and placebo arms. According to published results, the UTI rate in the placebo arm was 32% and approximately a 14-15% reduction was observed in the treatment arm. Using this information, we designed our study to mimic these findings, and assumed a UTI reduction rate of 18% in the nitrofurantoin arm could be observed in our clinical setting. Based on this assumption, total sample size of 164 patients was projected to achieve 80% power with a two-sided  $\alpha$  error of 0.05. We increased the total sample size to 180 to allow for a 10% dropout rate. However, due to primary investigator timeline and lack of attrition, recruitment ceased once the sample size of 164 was reached. The power was calculated by using the PASS 15 (2017, NCSS, LLC. Kaysville, Utah, USA). All analyses were conducted using an intent-to-treat principle, which included all women

randomized and not withdrawn from the study. A per-protocol analysis was also performed, and only included patients that completed the study.

Categorical data were compared using X or Fisher's Exact test where appropriate. Continuous variables were compared using Student's t-test or Wilcoxon rank sum where appropriate, and are presented as mean±standard deviation or median (interquartile range). We estimated risks for UTI with odds ratio (OR) and corresponding 95% confidence intervals (95% CI) calculated using logistic regression. A P value <0.05 defined statistical significance. All analyses were conducted using SAS Enterprise Guide version 7.1 (SAS Institute, Cary, NC). No interim analysis was performed.

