### **Study Withdrawal**

Participants may withdraw from the study at any point in time. Documentation of the reason for withdrawal will be captured in the data collection forms. There will be no risk to participants that choose to withdraw from the study.

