### **Week 2 Postoperative Visit (+/- 1 week)**

Participants will be scheduled for a 2-week postoperative follow up visit. They will be instructed to return their bottle of study medication and a medication compliance diary at this visit.

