## Treatment of UTIs

Urinary tract infection will be defined as:

- Any treatment received (outside of study drug) for clinically suspected UTI and/or a culture-proven UTI with a uropathogen within the first 30 days following surgery.
  - A urine culture is deemed positive if there are greater than 100,000 colony-forming units of a single organism. Urine cultures with mixed bacterial flora will **NOT** be classified as a positive culture.
  - Clinically suspected UTIs will be defined as dysuria, frequency, and irritation in the absence of vaginal discharge.

Study participants will not be eligible to take phenazopyridine while on study medications.

If a participant has clinical symptoms of a UTI during the study period, a urine specimen will be sent for culture and treatment will be based on appropriate antibiotics regarding specific susceptibilities. Per the IDSA guidelines, the following duration of treatment guidelines will be followed:

- 7-14 days duration of antimicrobial treatment for patients with a catheter-associated UTI, regardless of whether the catheter is in place or not
- A 3-day antimicrobial regimen may be considered for women aged 65 years old or less who develop a catheter-associated UTI after the catheter has been removed

The investigator will maintain discretion to deviate from these guidelines pending clinical reasons.

The participant will be treated empirically for seven days with one of the following antibiotics while awaiting urine culture results, based on personal treatment history, contraindications, and allergies:

- Cephalexin (500mg every 12 hours for 7-14 days) by mouth OR
- Fosfomycin (3 grams once) by mouth OR
- Ciprofloxacin (250 mg every 12 hours for 3 days OR 250-500mg every 12 hours for 7-14 days) by mouth

Fosfomycin is a single dose regimen. Although the IDSA recommends a 3-day or 7-14 day treatment course, recent in-vitro studies indicate that a single dose of fosfomycin is also effective and cost effective. Fosfomycin was demonstrated to have high bactericidal activity against biofilms on siliconized latex catheters. Therefore, it will also be offered as a treatment option for UTI to our participants.

Urine cultures will be obtained with susceptibilities, and antibiotic treatment may be changed depending on resistance. Once the uropathogen is known, the appropriate antibiotic regimen to treat the known uropathogen will be employed.

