If a participant is being empirically treated for a UTI, and the urine culture returns negative, the participant will be notified and instructed to stop taking the antibiotics.

The triage nursing staff, both in office and through the nursing phone triage service will receive study training prior to study commencement. Any participant that contacts our office outside of normal business hours with concerns of a UTI will be triaged and empirically treated with one of the appropriate antibiotics listed above. If they receive treatment from another provider outside our hospital system, authorization for release of records will be needed to be signed by the participant.

Any participant that has a positive urine culture from an outside provider, or is treated based on clinical symptoms without evidence of a positive urine culture will be deemed a treatment failure. These participants will be included in the study analysis as treatment failures.

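### The analysis set called intent-to-treat leaves out randomised women who withdrew, can drop UTI events the protocol says to count, and has no rule for an unknown 30-day outcome

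*Combined protocol and SAP*

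**What the plan says.** The set is defined in Statistical Considerations: "All analyses were conducted using an intent-to-treat principle, which included all women" "randomized and not withdrawn from the study" (one sentence, split by a page break). A per-protocol analysis is added, restricted to patients who completed the study; completion is not defined. The same section explains the final size: "due to primary investigator timeline and lack of attrition, recruitment ceased once the sample size of 164 was reached". It gives no number of withdrawals and does not say whether 164 counts women randomised or women analysed.

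Three other sections bear on this:

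- **Study Withdrawal:** "Participants may withdraw from the study at any point in time". Only the reason is to be documented. Nothing is said about data already collected.
- **Treatment of UTIs:** the endpoint covers treatment for a clinically suspected UTI and/or a "culture-proven UTI with a uropathogen within the first 30 days following surgery". Any participant who has a positive culture from an outside provider, or who "is treated based on clinical symptoms without evidence of a positive urine culture will be deemed a treatment failure", is a failure, and "These participants will be included in the study analysis as treatment failures". No exception is made for withdrawal.
- **Week 2 Postoperative Visit:** "Participants will be scheduled for a 2-week postoperative follow up visit", with a window of one week either side. No later scheduled contact is described in the text. Figure 1 is not shown in the copy reviewed and may describe one.

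**The concern.** A reader who sees intent-to-treat will assume that every randomised woman is in the comparison. Here she is in only if she did not withdraw. Withdrawal after the first dose can be related to treatment (side effects) or to outcome (a UTI treated elsewhere), so removing these women can bias the comparison. The documents do not settle in which direction.

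Two gaps make this more than a matter of labelling. First, for a woman who has a UTI and later withdraws, the two sections give opposite instructions: one counts her as a failure, the other removes her. Second, a woman may stay in the study and still have no known status at day 30, and no rule says how she is analysed.

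The per-protocol analysis may add little as a check. If withdrawal is the main way of not completing the study, the two sets nearly coincide.

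**Working it through.** **Inputs.** From Statistical Considerations: placebo UTI rate 32%, reduction of 18%, two-sided alpha 0.05, power 80%, total 164. Assumptions: equal arms, and every withdrawal or missing count below, since the documents give none. All p-values are Pearson chi-square without continuity correction. Placebo is listed first.

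**The plan's own figure.** Reading 18% as percentage points (32% to 14%), with unpooled variance:

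(1.960 + 0.842)² × (0.32×0.68 + 0.14×0.86) / 0.18² = 81.9, so 82 per arm and 164 in total.

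This reproduces the plan and supports 82 per arm at 32% and 14% as the base case. In whole women that is 26/82 vs 11/82: 18.3 points, p=0.0051.

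**(a) Women who had a UTI, then withdrew and were dropped.** Each is removed from numerator and denominator.

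| Dropped | Counts | Difference (points) | p |
|---|---|---|---|
| None | 26/82 vs 11/82 | 18.3 | 0.0051 |
| 2, nitrofurantoin only | 26/82 vs 9/80 | 20.5 | 0.0016 |
| 4, nitrofurantoin only | 26/82 vs 7/78 | 22.7 | 0.0004 |
| 2, placebo only | 24/80 vs 11/82 | 16.6 | 0.0103 |
| 4, placebo only | 22/78 vs 11/82 | 14.8 | 0.0208 |
| 4 in each arm | 22/78 vs 7/78 | 19.2 | 0.0020 |

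The estimate moves by 14.8 − 18.3 = −3.5 to 22.7 − 18.3 = +4.4 points. The conclusion does not change.

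**(b) Unknown outcomes, same rule in both arms.** With k women unknown per arm, observed events are 32% and 14% of 82 − k, rounded. The first column of p-values excludes the k women; the other two keep all 164.

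| k per arm | Excluded | All counted as UTI | None counted as UTI |
|---|---|---|---|
| 2 | 26/80 vs 11/80, p=0.0049 | 28/82 vs 13/82, p=0.0068 | 26/82 vs 11/82, p=0.0051 |
| 4 | 25/78 vs 11/78, p=0.0078 | 29/82 vs 15/82, p=0.0136 | 25/82 vs 11/82, p=0.0083 |
| 8 | 24/74 vs 10/74, p=0.0062 | 32/82 vs 18/82, p=0.0176 | 24/82 vs 10/82, p=0.0070 |

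Over k = 1 to 8 with all 164 kept, the largest p is 0.0266 (k=7, all counted as UTI, 31/82 vs 18/82).

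**(c) Worst case for the drug.** Every unknown nitrofurantoin woman has a UTI and no unknown placebo woman does.

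- k=2: 26/82 vs 13/82, p=0.0171
- k=3: 25/82 vs 14/82, p=0.0436
- k=4: 25/82 vs 15/82, p=0.0690

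The crossing point is sensitive to rounding: 26 placebo events instead of 25 at k=4 gives 26/82 vs 15/82, p=0.047. The opposite extreme gives p=0.0018 at k=2 and 0.0011 at k=4.

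**(d) A smaller effect than designed.** With hypothetical counts of 26/82 vs 16/82, p=0.074. Dropping two nitrofurantoin women with a UTI gives 26/82 vs 14/80, p=0.036. These counts were chosen near the threshold; they show that the set can decide the result, not that it did.

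**Can an outcome be unknown?** The scheduled visit falls between day 7 and day 21, which is 30 − 21 = 9 to 30 − 7 = 23 days before the end of the outcome window. Treatment outside the hospital system is confirmed through a release that the participant must sign, and no fallback is given if she does not.

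**The case against.** The strongest reply is that this may have no practical effect. The lack of attrition is the only evidence in the documents, and it points to few withdrawals. Eight per arm (8/82 = 9.8%) would be about the whole 10% dropout allowance, so the low counts above are the more plausible. At the design rates only the one-sided worst case passes 0.05, and narrowly. This stands as a limit on size. It does not show that nobody was removed, because the phrase comes with no number and no split by arm.

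Second, the rule in Treatment of UTIs can be read as classifying outcomes within whatever set the statistics section defines, in which case there is no conflict. That reading is possible, but the rule covers any participant and says that she is included in the analysis. The clash is confined to women with both a UTI and a later withdrawal, and nothing shows that one exists.

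Third, withdrawal is not defined. Enrolment precedes surgery and randomisation follows a passed office voiding trial, so some withdrawals come before randomisation and do not touch this set. Withdrawn consent may also limit the use of later data, though it need not erase an event already recorded. Both points are fair, and they are reasons to define the term.

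Fourth, the endpoint is driven by events and is also captured through office and telephone triage and outside records, so the week-2 visit is not the only route. This makes unknown outcomes less likely; it does not supply a rule for them.

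**Conclusion.** The concern holds. The set named intent-to-treat is a modified intent-to-treat set. Taken literally, its definition contradicts the treatment-failure rule for a woman who has a UTI and then withdraws, and no rule is written for an unknown 30-day outcome. The first point is certain from the text and carries the finding. The missing-outcome rule, the undefined completion criterion and the status of 164 are gaps in detail.

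The effect on the result is unknown and possibly nil. Under the assumed 32% vs 14% with 82 per arm, the scenarios in (a) move the estimate by −3.5 to +4.4 points without changing the conclusion. Only the worst case for the drug exceeds 0.05, at around four unknown outcomes per arm. A smaller true effect would leave less room. If no randomised woman withdrew, the set needs only a corrected label. It should be fixed, but it is not evidence that the result is wrong.

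**What to change.** 1. Make the primary analysis all randomised women in the arm assigned. Keep the present set as a sensitivity analysis, named modified intent-to-treat.
2. Count any UTI treatment or positive culture known before withdrawal as an event, in line with Treatment of UTIs. Define withdrawal, separating stopping capsules, withdrawn consent and loss to follow-up.
3. Where the 30-day outcome is unknown, use records as far as consent or signed authorisation permits, and give a best-case/worst-case range for the rest.
4. State whether 164 is randomised or analysed, and report withdrawals and unknown outcomes by arm.
5. Define completion for the per-protocol set. Label any adherence threshold added now as post hoc, particularly since the Randomization section leaves the statistician unmasked.

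The cost is a wording change and a small re-analysis, because the section is already written in the past tense. The planned size, treatment and visits do not change. The estimate may become less favourable to the drug, and some outcomes may stay unknown where no release is signed.

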## BACKGROUND

Urinary tract infections (UTI) are the most common hospital-acquired infections, accounting for nearly 30% of cases of nosocomial infections and affecting nearly 1 million people per year. They account for nearly 8.1 million visits to health care providers and cost an estimated \$1.6 billion a year in the United States alone.

Following pelvic reconstructive and urinary incontinence surgery, UTIs are one of the most common complications. The baseline risk of UTI associated with pelvic floor surgery ranges between 5-35%, increasing greatly with catheterization. In women who are undergoing surgery for urinary incontinence, the risk of UTI ranges between 8.9% to 34%. Risk factors for urinary tract infections in women undergoing pelvic floor and urinary incontinence surgery include: history of recurrent UTI, longer operative times, and increased duration of postoperative catheterization.

Postoperative voiding dysfunction and incomplete bladder emptying is common following pelvic reconstructive and incontinence surgeries, with incidence ranging from 2.5 % to 31%. As a result, these women may have additional catheterization for a short period of time, which increases the risk of UTI. There is a 15-20% risk of developing a postoperative UTI with short-term catheterization, even if the catheter remains in place for merely 24 hours. The risk of UTI increases 5-10% each day the catheter is left in place. In the SISTEr trial, which was a multicenter, prospective, randomized trial comparing Burch colposuspension versus autologous fascial slings for the treatment of stress urinary incontinence, catheter usage postoperatively for incomplete bladder emptying resulted in an increased rate of UTIs. Participants who underwent the fascial sling (48%) had more UTI events (305) compared with the 32% of women in the Burch colposuspension group (203) ( $p < 0.001$ ).

This was concluded to be secondary to the prolonged need for catheterization due to postoperative voiding dysfunction.

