## **STUDY DESIGN AND METHODS**

This is a randomized, double-blind, placebo-controlled trial offered to patients who receive postoperative short-term transurethral catheterization after undergoing surgery for pelvic organ prolapse (POP), urinary incontinence, or both. The study will be conducted at two clinical sites:

1. Women's Center for Pelvic Health (Mercy), Atrium Health, Charlotte, NC
2. Women's Center for Pelvic Health (NorthEast) Atrium Health, Concord, NC

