### **In Office Voiding Trial**

Participants who are discharged with an indwelling Foley catheter will be scheduled to return to the office in 1-7 days for an in-office retrograde voiding trial. All office personnel (nurses, medical assistants, physicians, physician's assistants, and nurse practitioners) will receive education regarding voiding trial technique as outlined below prior to study commencement.

The bladder will be retrograde filled with normal saline up to a maximum of 300mL, and the catheter will then be removed. The participant will attempt to void immediately, but the participant will have up to 60 minutes to attempt voiding. After voiding, the participant will be asked to complete a Force of Stream questionnaire. The urine will be measured and a post-void residual will be obtained with a bladder scan. If urine voided is 200 mL or greater, and the post-void residual is less than one-third of the total amount (voided volume plus residual volume), the catheter will be left out and the participant will be considered a voiding trial pass. If the volume is less than 200 mL, and the post-void residual is greater than one third of the total amount, the participant will be deemed a voiding trial failure; these patients will be sent home with a Foley catheter. After completing a bladder scan immediately after voiding attempt, the provider will be notified of the voided volume and post-void residual (to be obtained by bladder scan).

Once a participant has successfully passed the voiding trial, they will be eligible for randomization.

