### **Randomization**

Randomization will be controlled by the Carolinas HealthCare System Investigational Drug Services pharmacy through random permuted blocks and stratified per site. The biostatistician will generate the randomization sequence and provide this information to the pharmacist.

The study will be double-blinded such that both study participants and investigators will be masked to treatment allocation and block size randomization, except for the pharmacist and statistician, who will have no contact with the patients.

The Investigational Drug Services (IDS) pharmacy will provide blinded medication bottles containing either nitrofurantoin or placebo 100mg capsules. Each bottle will

contain 10 capsules. These bottles will be labeled by the IDS pharmacy with a randomization number. The study medications will be released by the pharmacy to the research nurse, who is also blinded. The medication bottles will be stored in a locked cabinet in a climate-controlled room until dispensed.

Eligible participants that have successfully passed the in-office voiding trial will be randomized into one of two groups upon completion of the voiding trial data collection sheet. There will be no indication which group the participant was randomized to. These sheets will be fluorescent colored and a part of each participant's chart. This sheet will need to be completed by the nurse administering the voiding trial.

The participants randomized to Group A will receive 100 mg nitrofurantoin every 12 hours by mouth starting on the day the Foley catheter is removed and complete a five-day course. Conversely, participants randomized into Group B will receive a matched placebo every 12 hours each day starting on the date of Foley catheter removal, for five days. Again, there will be no indication which group the participant was randomized to.

At the time of randomization, the participant will be assigned a randomization number. The bottle of medication with the same corresponding randomization ID will be dispensed. This will be a bottle of 10 capsules of nitrofurantoin or matching placebo with instructions to take every 12 hours for five days. The first dose will be given in the office. Participants will be asked to complete a one-week medication diary. Participants will be asked to return this bottle of medication, any unused medication, and a medication compliance diary at the first postoperative visit following surgery.

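### Randomisation is stratified by site, but the planned UTI analysis names no site term; analyse the primary outcome by site

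*Combined protocol and SAP*

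**What the plan says.** - **Allocation.** Under Randomization, allocation is made "through random permuted blocks and stratified per site". Under Study Design and Methods, "The study will be conducted at two clinical sites".
- **Test.** Statistical Considerations compares categorical data, which includes UTI, by chi-square "or Fisher's Exact test where appropriate". It names no strata.
- **Estimate.** The same section states: "We estimated risks for UTI with odds ratio (OR) and corresponding 95% confidence intervals (95% CI) calculated using logistic regression". It lists no covariates.
- **Sizing.** The section takes a placebo UTI rate of 32% and "assumed a UTI reduction rate of 18% in the nitrofurantoin arm". It projects 164 women for 80% power at two-sided 0.05.
- **Timing.** The section is in the past tense and reports that "recruitment ceased once the sample size of 164 was reached".

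No other section mentions site adjustment, a stratified test or a risk difference.

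**The concern.** Blocking within site balances the arms inside each site, which removes differences between sites from the treatment comparison. An unstratified variance still counts those differences. If the sites have different UTI rates, the unstratified test is conservative and its interval is slightly too wide, so part of the benefit of stratifying is lost.

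Two related gaps sit in the same section:

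- The choice between chi-square and Fisher is left open for the primary outcome.
- The trial was sized on an absolute difference in UTI rates, but the only UTI effect measure named with an interval is an odds ratio. At the design rates the odds ratio is 0.35 and the risk ratio is 0.14/0.32 = 0.44. A reader who takes the first for the second would overstate the benefit.

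**Working it through.** **Inputs from the documents.** Two sites, site-stratified blocks, placebo rate 32%, reduction 18%, two-sided alpha 0.05, power 80%, N = 164.

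**Assumptions.** 1:1 allocation (82 per arm), the split of women between sites, and the size of any site effect. The documents give none of these.

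**1. The plan's own figure.** Read the 18% as percentage points, so 32% against 14%. The unpooled two-proportion formula gives

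n per arm = (1.96 + 0.8416)² × (0.32×0.68 + 0.14×0.86) / 0.18² = 81.9, so 82 per arm and 164 in total.

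This matches. Other readings do not (pooled-variance normal formula): 32% against 18% gives 298, and an 18% relative reduction gives 1,952. The treatment odds ratio is (0.14/0.86)/(0.32/0.68) = 0.346.

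**2. Why the size falls when site is ignored.** Take equal sites with a common rate of 32% in both arms.

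- Variance the unstratified test uses: 0.32×0.68 = 0.2176.
- Variance that remains within sites, at rates of 17% and 47% (site odds ratio about 4.3): (0.17×0.83 + 0.47×0.53)/2 = 0.1951.
- Ratio of standard errors: √(0.1951/0.2176) = 0.947.
- Effective critical value: 1.96/0.947 = 2.07, which is a two-sided size of about 3.8%.

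The simulation below gives 3.9%.

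**3. Chi-square against CMH by site.** Neither test uses a continuity correction. There were 400,000 runs per setting, 41 + 41 women per arm, the placebo rate held at 32% overall, and a treatment odds ratio of 0.346 within each site.

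| Site odds ratio | Size: chi-square / CMH | Power: chi-square / CMH | CMH gain (points) |
|---|---|---|---|
| 1 | about 5% for both | 79.6% / 79.4% | -0.2 |
| 1.5 | 4.9% / 5.1% | 79.1% / 79.1% | 0.0 |
| 2 | 4.7% / 5.0% | 78.4% / 78.8% | +0.4 |
| 2.6 | 4.4% / 4.9% | 77.5% / 78.4% | +0.9 |
| 4.3 | 3.9% / 5.0% | 74.6% / 76.9% | +2.3 |

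Power falls down the table for both tests because a fixed within-site odds ratio gives a smaller overall difference as the sites diverge.

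- **Unequal sites.** With 57 + 25 women per arm, the gain at odds ratio 4.3 is 76.6 - 73.8 = 2.8 points from the rounded powers (2.7 before rounding).
- **Overall rates fixed.** With both arms held at 32% and 14% overall and equal sites, the gains are -0.2, 0.0, +0.3, +0.8 and +2.0 points.
- **Independent re-run.** A run with 41/41 and 62/20 splits and site log-odds gaps up to 2.0 found the same pattern: CMH size near 5% throughout, and no larger N needed.

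**4. Estimates by site.** There were 100,000 runs per setting.

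- Logistic regression on arm and site has size 4.8–5.1% (Wald) or 5.1–5.3% (likelihood ratio).
- The 95% interval half-width for the risk difference, unstratified against Mantel-Haenszel by site, is 12.5 against 12.4 points at site odds ratio 2, and 12.6 against 12.2 at 4.3.
- The stratified interval covers 94.7–94.8%.

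**5. Chi-square or Fisher.** By exact enumeration at 82 per arm, power is 79.6% for chi-square and 73.7% for Fisher, a gap of 5.9 points. Size at null rates of 14–32% is 4.9–5.1% for chi-square and 3.0–3.4% for Fisher. Taking the most favourable of chi-square, Fisher and Wald logistic gives 4.9–5.1%, or up to 5.3% if the logistic test is the likelihood ratio, so open choice among them adds little error. Expected UTI counts at the design rates are 82×0.32 = 26 and 82×0.14 = 11, or about 19 per arm pooled, so small cells give no reason to use Fisher.

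**The case against.** The strongest reply is that nothing material follows. Size is near nominal, the error is in the safe direction, and up to a site odds ratio of 2 the power gain is between -0.2 and +0.4 points. The larger gains need site rates such as 17% and 47%. Both sites are women's pelvic health centres of one health system, with the same eligibility criteria, one voiding-trial technique and trained staff, so a gap that wide is an extreme case. This stands, and it limits the size of the claim.

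Second, the logistic model may have contained site, because the plan lists no covariates either way. That is possible, but a reader cannot tell, and the tests named are unstratified.

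Third, the usual small-expected-count reading of the Fisher wording would select chi-square for UTI, and Fisher has a proper use for sparse adverse events. This also stands: the loss of about 6 points is an unlikely outcome, and naming the test is a precaution.

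Fourth, an odds ratio is a legitimate effect measure. Agreed; the risk difference is an addition that reports the quantity used for sizing.

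Finally, if the data are already unblinded, the adjusted analyses can only be supplementary. This is right and is built into the fix. None of these points removes the mismatch between how women were randomised and how the outcome is analysed.

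**Conclusion.** The concern holds. The stated UTI analysis ignores the one factor used to stratify randomisation. The result is a slightly conservative test, with size 4.4–4.9% for site odds ratios of 1.5 to 2.6 and 3.9% at 4.3. The power cost is nil to 0.4 points unless the sites differ a lot, and about 2 to 3 points at odds ratio 4.3. If the sites do not differ, stratifying costs about 0.2 points. Validity, N = 164 and the likely conclusion are unaffected. The figures assume 82 per arm, the design rates of 32% and 14%, and hypothetical site splits and site effects. This is a worthwhile, nearly free improvement and not a threat to the trial.

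**What to change.** Analyse the primary UTI outcome by the randomisation strata:

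1. Use the CMH test by site as the main test.
2. Give the odds ratio and 95% confidence interval from logistic regression on arm and site, described as conditional on site.
3. Add a site-stratified (Mantel-Haenszel) risk difference with its 95% confidence interval.
4. Keep the unadjusted chi-square as supportive. If a test other than CMH is kept as the main one, name the uncorrected chi-square and not Fisher.

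**Timing condition.** If the site-adjusted analysis was not fixed before unblinding, keep the unadjusted chi-square as the main result and label the adjusted analyses post hoc. In either case, state whether site was in the logistic model.

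**Optional.** Background lists as risk factors "history of recurrent UTI, longer operative times, and increased duration of postoperative catheterization". Days from surgery to catheter removal is known at allocation, because "Once a participant has successfully passed the voiding trial, they will be eligible for randomization". A supportive model may add it, with its odds ratio described as conditional on site and days. No power gain is claimed. The documents do not give the gradient or distribution of catheter days, women with a UTI while catheterised are excluded, and the 30-day window starts at surgery.

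**Cost.** A few lines in the analysis section and a few lines of SAS. Site is known for every randomised woman, and no more women are needed. The downsides are about 0.2 points of power if the sites are alike, and an odds ratio that is conditional on site instead of marginal.
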